Assuming 100 subjects enrolled per group, and after accounting for a maximum of 5% subjects for whom serological results might not be available, 95 evaluable subjects per group are expected. The estimated number of strains to be tested per sample is approximately 35 (range 33-37), based on a 50% re-test rate. With 95 evaluable subjects in a group, this translates into approximately 30 (range 28-32) samples for assessment of VE for each strain and 3325 (range 3135-3515) total measures for the overall VE, for that group.

Assuming 56 subjects enrolled per group, and after accounting for a maximum of 5% subjects for whom serological results might not be available, 50 evaluable subjects per group are expected. The estimated number of strains to be tested per sample is approximately 35 (range 33-37), based on a 50% re-test rate. With evaluable subjects in a group, this translates into approximately 16 (15-17) samples for assessment of VE for each strain and 1750 (range 1650-1850) total measures for the overall VE, for that group.

For each endemic US *N. meningitidis* serogroup B strain tested using the enc-hSBA, vaccine effectiveness (VE) of 3 doses of MenABCWY compared to 2 doses of MenABCWY will be defined as VE = [1 - (percentage of subjects without bactericidal serum activity at 1:4 dilution using enc-hSBA in MenABCWY group receiving 3 doses /

percentage of subjects without bactericidal serum activity at 1:4 dilution using enc-hSBA in MenABCWY group receiving 2 doses)] x 100. For the primary and secondary effectiveness endpoints for the 110 strains combined, the overall VE will be obtained by pooling across 110 individual strain-specific VE measures.

For the primary and secondary effectiveness endpoints, a log binomial model will be estimated, with binary outcome "having/not having bactericidal serum activity at 1:4 dilution using enc-hSBA" for each strain tested within each subject. Treatment group and strain will be included as independent variables. The VE and associated 95% CI will be computed from this model. A Poisson regression with a robust error variance will be estimated as an alternative, to account for the clustering of data and in case of difficulties in convergence of the log binomial model.

Table 8.5-1 displays the power for a constant VE. Since this study evaluates persistence at approximately 2 years after the last meningococcal vaccination in the parent study, no relevant differences between low—and high-respondent strains are expected to be found at this point in time. As a consequence, no computations with varying VE assumptions are made.

Table 8.5-1: Power for overall VE against all 110 strains combined (95 subjects per group, 50% re-test rate)

% subjects without bactericidal se			
2 doses MenABCWY (0,2 month schedule)	3 doses MenABCWY (0,2,6- month schedule)	VE	Power*
60%	50%	17%	0%
60%	40%	33%	>99%
60%	30%	50%	>99%
60%	20%	67%	>99%
60%	10%	83%	>99%

Lower bound of the two-sided 95% confidence interval for VE above 20%.

Approximately 35 strains tested per sample (range 33-37), based on a 50% re-test rate. With 95 evaluable subjects in a group, this translates into approximately 30 (range 28-32) samples for assessment of VE for each strain.

**Computed from 10,000 simulation runs, each based on SAS PROC GENMOD using the statistical method proposed in Section 1.2.

For the overall VE, this study with 3325 measures per study group (average of 30 samples per strain and 110 strains) will provide >99% power to detect an overall VE of 33% against the panel of the endemic US *N. meningitidis* serogroup B strains with the lower limit of the two-sided 95% confidence interval >20%. Even with a much smaller number of samples (e.g. 50 subjects, 1750 samples) the power of the study would not change and would be >99% to detect and overall VE of 33% with a lower limit of two-sided 95% confidence interval >20%.

Table 8.5-2 provides the power for different values of strain-specific VE, assuming 30 samples for assessment per strain:

Table 8.5-2: Power for strain-specific VE (95 subjects per group, 50% re-test rate)

% subjects without bactericidal			
2 doses MenABCWY (0,2-month schedule)	3 doses MenABCWY (0,2,6- month schedule)	VE	Power*
60%	40%	33%	7.6%
60%	30%	50%	28.5%
60%	20%	67%	65.7%
60%	10%	83%	94.0%
80%	60%	25%	3.1%
80%	50%	38%	16.6%
80%	40%	50%	47.9%
80%	30%	63%	81.9%
80%	20%	75%	97.7%

Lower bound of the two-sided 95% confidence interval for VE above 20%.

Approximately 35 strains tested per sample (range 33-37), based on a 50% re-test rate. With 95 evaluable subjects in a group, this translates into approximately 30 (range 28-32) samples for assessment of VE for each strain.

Computed from 10,000 simulation runs, each based on SAS PROC GENMOD using the statistical method proposed in Section 1.2.

For each strain, if the percentage of subjects without bactericidal serum activity at 1:4 dilution (enc-hSBA > 4) in the MenABCWY group receiving 2 doses is at least 60%, 30 evaluable subjects per strain and study group will provide ≥94% power to detect a vaccine effectiveness of 83%. If the percentage of subjects without bactericidal serum activity at 1:4 dilution (enc-hSBA > 4) in the MenABCWY group receiving 2 doses is at least 80%, 30 evaluable subjects per strain and study group will provide ≥97% power to detect a vaccine effectiveness of 75%.

Considering a lower number of enrolled subjects (50 available subjects, 16 samples per strain), the above scenarios will provide study power of 61% and 75% respectively.

Power simulations have been done using PC SAS (SAS version 9.2).

In **Section 14**, **Reference list** the reference list was ordered alphabetically:

Clopper C J and Pearson ES. The use of confidential or fiducial limits illustrated in the case of the binomial. Biometrika; 26: 401-403. 1934.

Code of Federal Regulations (1997): Food and Drug Administration, U.S. Department of Health and Human Services: Title 21, Part 11: Electronic Records Electronic Signatures. Federal Register 62: 13464

European Parliament (1995): Directive 95/46/EC of the European Parliament and of the Council of 4 April 2001. Official Journal of the European Communities. L 281/31-39

European Parliament (2001): Directive 2001/20/EC of the European Parliament and of the Council of 4 April 2001. Official Journal of the European Communities. L 121/34-44

ICH (1997) ICH Harmonised Tripartite ICH Guideline for Good Clinical Practices E6 (R1). Federal Register, 62 (90): 25691-25709

ICH (1998) ICH Harmonised Tripartite ICH Guideline for Statistical Principles for Clinical Trials E9. Federal Register, 63 (179): 49583

Goldschneider, I., E. C. Gotschlich, and M. S. Artenstein. 1969. Human immunity to the meningococcus. I. The role of humoral antibodies. J. Exp. Med. 129:1307–1326.

Goldschneider, I., E. C. Gotschlich, and M. S. Artenstein. 1969. Human immunity to the meningococcus. II. Development of natural immunity. J. Exp. Med. 129:1327–1348.

# LIST OF ABBREVIATIONS

AE Adverse Event

ANOVA Analysis of Variance
CSR Clinical Study Report

CRDL Clinical Research and Development Lead

EXC excluded from this analysis set

FAS Full Analysis Set

IRT Interactive Response Technology

MedDRA Medical Dictionary for Regulatory Activities

PD Protocol Deviation
PPS Per Protocol Set

SAE Serious Adverse Event SAP Statistical Analysis Plan

SD Standard Deviation
SDL Study Delivery Lead
SP Statistical Programmer

TFL Tables, Figures and Listings

TOC Table of Content

# 1. BACKGROUND AND RATIONALE

This SAP version 2 is based on the response (submitted on 15 September 2017) to CBER comments (received on 26 October 2016), to change the defined criterion for concluding relative vaccine effectiveness, the Company agreed to remove it from the V102\_15E1 study protocol and all analyses for the vaccine effectiveness objectives to be descriptive in nature. Further to this decision, in this amendment the effectiveness of the MenABCWY vaccine using enc-hSBA will no longer be assessed in *any* of the V102\_15E1 study objectives (primary, secondary or exploratory). *All* the study objectives will aim to evaluate the immunogenicity of the MenABCWY vaccine against *N. meningitidis* serogroup B test strains (NZ98/254 (PorA), M14459 (fHbp), M07-0241084 (NHBA) and 96217 (NadA)) using HT-hSBA, accordingly.

For further details please refer to section 1.0 and appendix A of the protocol.

## 2. OBJECTIVES

## **Primary Immunogenicity Objectives**

1. To assess the persistence of bactericidal antibodies in subjects who previously received 2 or 3 doses of MenABCWY (administered according to 0, 2-, 0, 6- and 0, 2, 6-month schedules) or 2 doses of rMenB+OMV (given at a 0, 2-month schedule), at 24 months after the last meningococcal vaccination in study V102\_15 compared with baseline antibody levels in meningococcal naive subjects at enrolment, as measured by percentages of subjects with HT-hSBA titers ≥ LLOQ and HT-hSBA GMTs against N. meningitidis test strains for serogroup B¹ and serogroups A, C, W, and Y.

# Secondary Immunogenicity Objectives

- 1. To assess the immune response at Day 31 after a booster dose of the MenABCWY vaccine given 24 months after last meningococcal vaccination in subjects who previously received 2 or 3 doses of MenABCWY at different schedules (administered according to 0, 2-, 0, 6- and 0, 2, 6-month schedules) in study V102\_15 compared with the immune response at Day 31 after a single dose of MenABCWY in naive subjects, as measured by percentages of subjects with HT-hSBA titers ≥ LLOQ, percentages of subjects with four-fold rise² in titers and HT-hSBA GMTs against N. meningitidis serogroups A, C, W, Y and serogroup B test strains¹;
- 2. To assess the immune response at Day 1 (prevaccination), and at Day 6 and Day 31 after a booster dose of MenABCWY given at 24 months after last meningococcal vaccination in subjects who previously received 2 or 3 doses of MenABCWY at different schedules (administered according to 0, 2-, 0, 6- and 0, 2, 6-month schedules) in study V102\_15, and at Day 1 (prevaccination) and after 2 doses of MenABCWY (at Day 66 and Day 91) in naive subjects, as measured by percentages of subjects with HT-hSBA titers ≥ LLOQ, percentages of subjects

 Serogroup B test strains to be used in the study: NZ98/254 (PorA), M14459 (fHbp), M07-0241084 (NHBA) and 96217 (NadA).

<sup>2 For subjects with prevaccination hSBA titers < LLOQ, a post-vaccination hSBA  $\geq$  4 times the LLOQ; for subjects with prevaccination hSBA titers  $\geq$  LLOQ, an increase of at least 4 times the prevaccination hSBA.

with four-fold rise in titers and HT-hSBA GMTs against *N meningitidis* serogroups A, C, W, Y and serogroup B test strains;

- 3. To assess the immune response at Day 31 after a booster dose of the rMenB+OMV vaccine given 24 months after last meningococcal vaccination in subjects who previously received 2 doses of rMenB+OMV administered according to 0, 2-month schedule in study V102\_15 compared with the immune response at Day 31 after a single dose of rMenB+OMV in naive subjects, as measured by percentages of subjects with HT-hSBA titers ≥ LLOQ, percentages of subjects with four-fold rise³ in titers and HT-hSBA GMTs against *N. meningitidis* serogroup B test strains⁴;
- 4. To assess the immune response at Day 1 (prevaccination), and at Day 6 and Day 31 after a booster dose of the rMenB+OMV vaccine given 24 months after last meningococcal vaccination in subjects who previously received 2 doses of rMenB+OMV at 0, 2-month schedule in study V102\_15, and at Day 1 (prevaccination) and after 2 doses of rMenB+OMV (at Day 66 and Day 91) in naive subjects, as measured by percentages of subjects with HT-hSBA titers ≥ LLOQ, percentages of subjects with four-fold rise³ in titers and HT-hSBA GMTs against *N. meningitidis* serogroup B test strains⁴.

## **Safety Objectives**

Primary Objective:

N.A

Secondary Objectives:

1. To evaluate safety and reactogenicity of a booster dose of MenABCWY given 24 months after last meningococcal vaccination in subjects who previously received 2 or 3 doses of MenABCWY at different schedules (administered according to 0, 2-, 0, 6-

 For subjects with prevaccination hSBA titers < LLOQ, a post-vaccination hSBA  $\geq$  4 times the LLOQ; for subjects with prevaccination hSBA titers  $\geq$  LLOQ, an increase of at least 4 times the prevaccination hSBA.

<sup>4 Serogroup B test strains to be used in the study: NZ98/254 (PorA), M14459 (fHbp), M07-0241084 (NHBA) and 96217 (NadA).

- and 0, 2, 6-month schedules) in study V102\_15, and after a first dose of MenABCWY in naive subjects;
- 2. To evaluate safety and reactogenicity of a booster dose of rMenB+OMV given 24 months after last meningococcal vaccination in subjects who previously received 2 doses of rMenB (administered according to 0, 2-month schedule) in study V102\_15 and after a first dose of rMenB+OMV in naive subjects;
- 3. To evaluate safety and reactogenicity of 2 doses of MenABCWY or rMenB+OMV in naive subjects.

# 3. STUDY DESIGN

For further details please refer to section 3.0 of the protocol.

Page 9 of 48

Table 3.1-1: Study Groups/planned sample size in V102\_15E1

	02_15 ary Study)	V102_15E1 24 months after last meningococcal vaccination in parent study				
Group	Group Vaccine (schedule)		Number of Subjects* (target enrolment)			
ABCWY_0_2	MenABCWY (0, 2 months)	ABCWY_0_2	up to 196 (100)			
ABCWY_0_2_6	MenABCWY (0, 2, 6 months)	ABCWY_0_2_6	up to 130 (100)			
B_0_2	rMenB+OMV (0, 2 months)	B_0_2	up to 196 (100)			
ABCWY_0_6	MenABCWY (0, 6 months)	ABCWY_0_6	up to 130 (100)			
		Naive (freshly enrolled)	200 (200)			

\*Maximum enrolment derived from planned enrolment per group in parent trial; Target enrolment is based on minimum number of subjects required for enchSBA testing.

Table 3.1-2: V102\_15E1 Blood Draw and Vaccination Schedule for follow-on subjects

	Target		Day 1	Day 6	Day 16		Day 31	Day 91	Day 181
Group	enrolment	Blood Draw	Vaccination	Blood Draw				Phone Call for Safety Assessment	Phone Call for Safety
ABCWY_0_2	100	20 mL	MenABCWY	20 mL	Phone call	20 mL	Safety Evaluation	Safety Evaluation	
B_0_2	100	20 mL	rMenB+OMV	20 mL		20 mL			Termination

2	,
	Pag

ABCWY_0_2_6	100	20 mL	MenABCWY	20 mL	20 mL
ABCWY_0_6	100	20 mL	MenABCWY	20 mL	20 mL

# Table 3.1-3: V102\_15E1 Blood Draw and Vaccination Schedule for Naive subjects

			Day 1	Day 16	Day 31	Day 61	Day 66	Day 76	D	ay 91	Day 151	Day 241
	N	Blood Draw	Vaccination	Safety	Blood Draw	Vaccination	Blood Draw	Safety	Blood Draw		Phone Call for Safety Assessment	Phone Call for Safety
Naive_ABCWY	100	20 mL	MenABCWY	Phone call	20 mL	MenABCWY	20 mL	Phone call	20 mL	Safety Evaluation		Assessment and Study
Naive_B	100	20 mL	rMenB+OMV		20 mL	rMenB+OMV	20 mL		20 mL			Termination

# 4. RANDOMIZATION AND BLINDING

# 4.1 Method of Group Assignment and Randomization

For further details please refer to section 5.1.4 of the protocol.

#### 4.1.1 Definition of Randomization/Vaccination Errors

The list below provides some examples of potential errors that may occur during vaccination:

- Subjects got vaccinated with a vaccine different from the one assigned at randomization (PD code 120)
- Subjects got vaccinated with the correct vaccine but containing a lower volume (PD code 140.3)

A misrandomization is defined as a subject receiving a vaccine other than the one assigned by randomization. Misrandomization is a Clinical Study Report (CSR)-reportable Protocol Deviation (PD) and should be analyzed as randomized in Full Analysis Set (FAS), excluded from Per Protocol Set (PPS) and analyzed as received for Safety.

Please see section 7 of this document for a complete guidance on how vaccination errors are handled in the statistical analysis.

## 4.1.2 Forced Randomization

In case of supplies shortage for the next assigned vaccine according to the randomization schedule at the clinical site, the IRT system will use the forced randomization procedure in order to continue to enroll and vaccinate subjects. The system moves seamlessly to the next treatment/randomization number for which vaccine supplies are available. The site will not be aware of the forced randomization event.

The forced randomization mechanism is designed in such a dynamic way that once the inventory is fulfilled it will balance the treatment groups according to the randomization ratio. Forced randomization should be minimized by proactively preventing the supplies inventory shortage.

A forced randomization will not be considered a protocol deviation. However a sensitivity analysis should be performed to evaluate its impact, when >1% of subjects have been randomized by forced randomization.

# 4.2 Blinding and Unblinding

Not Applicable.

# 5. SAMPLE SIZE AND POWER CONSIDERATIONS

For details please refer to section 8.5 of the protocol.

Sample size/power considerations are included in the study protocol. Technical details including statistical assumptions and software are given in a separate sample size memo authored by the study Biostatistician. In the same document, a PRC statistical reviewer verified and documented the sample size/power considerations. This document was completed prior to finalization of the protocol and stored in eTMF.

# 6. DETERMINATION OF PROTOCOL DEVIATIONS

#### **6.1** Definition of Protocol Deviations

CSR reportable PD are defined in accordance with ICH E3 as important PDs related to study inclusion or exclusion criteria, conduct of the trial, subject management or subject assessment resulting in the potential to jeopardize the safety or rights of the trial subjects or the scientific value of the trial.

All reportable PDs will be evaluated before the analysis and classified according to ICH into the following five categories:

- Subject developed withdrawal criteria during the study but was not withdrawn
- Underlying medical condition forbidden by the protocol or which may influence immune response (PD code 240).
- Subject had contraindication for a subsequent study vaccination but was vaccinated (PD code 220).
- Concomitant infection related to the vaccine which may influence immune response (PD code 250).
- Subject received wrong vaccine or incorrect dose
- Study vaccine was not administered at all (PD code 100)
- Vaccine administration not according to protocol (PD code 140.x).
- Randomization failure (vaccination not according to randomization) (PD code 120).
- Subject took an excluded concomitant medication
- Administration of concomitant vaccine(s) forbidden in the protocol (PD code 150.x).
- Administration of any medication forbidden by the protocol (PD code 230.x).
- Subject randomized and did not satisfy the entry criteria
- Subject did not meet entry criteria (PD code 200).
- Deviation from key study procedures
- Subject did not comply with study vaccination schedule (PD code 140.x).
- Subject did not provide any post-vaccination unsolicited safety data (PD code 115.x).

- Subject did not provide any post-vaccination solicited safety data (PD code 116.x).
- Subject did not comply with blood draw schedule (PD code 270.x).
- Serological results not available post-vaccination (PD code 110.x).
- Obvious incoherence, abnormal serology evolution or error in data (PD code 112).

CSR reportable PDs will lead to exclusion of the subject or part of the subject's data from at least one analysis set.

The number of subjects in any and by PD category will be summarized by vaccine, center and overall. Individual subject listings will be provided in an appendix, sorted by subject and by PD category.

Prior to the analysis, designated GSK staff will develop a memo that describes the PDs that led to exclusions from analysis sets. This memo will be signed off by at least the Biostatistician and the Cluster Physician and will be included in the trial master file (Exclusion Memo).

Prematurely terminating study participation for reasons such as withdrawal of consent or occurrence of adverse events (including death) is not considered as a PD. The missing assessments that should have otherwise been collected for that subject later in the study are also not considered as a PD.

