8.3.5 Per Protocol (PP) Set Immunogenicity Set

Per Protocol (PP) Set Immunogenicity

All subjects in the FAS Immunogenicity who:

- Correctly receive all meningococcal vaccinations in the parent study (persistence objective) /all meningococcal vaccinations in the parent study and vaccinations relevant for the objective¹ in the extension study (rest of immunogenicity objectives) and,
- Have no protocol deviations leading to exclusion (see section 8.3.8, Protocol Deviations) as defined prior to analysis and,
- Are not excluded due to other reasons defined prior to analysis (see section 8.3.8, Protocol Deviations).

Additional requirements:

Per Protocol Set Immunogenicity (Days 6 and 31, after booster dose [follow-on]/ Days 66 and 91 after second dose [naive]) – PPS Immunogenicity (Days 6, 31/Days 66, 91)

All subjects in the PPS *Immunogenicity* who:

• Provide evaluable serum sample with results for at least one serogroup B test strain or serogroups A, C, W or Y (only after MenABCWY vaccination) at Day 1, Day 6 and Day 31 (follow-on subjects) / Day 1, Day 66 and Day 91 (naive subjects) in the extension study.

PPS are subsets of FAS and should be always defined even if the objectives do not require it.

¹ Booster dose (follow-on) and first dose (naive in secondary objectives *1* and *3*) / first and second dose (naive in secondary objectives *2* and *4*). Further details will be provided in the Statistical Analysis Plan.

Subjects might be excluded due to other reasons than protocol deviations (e.g., subjects who withdrew informed consent).

(Amended 4 April 2018)

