110.d.502	Serology results are not available Serological results (A, C, W, Y and 4 B strains) are not available	Day 91			EXC (naive only)			EXC (naive only)
112.102	Obvious deviation from Laboratory Manual or error in laboratory data (HT-SBA)	Day 1				EXC		EXC
112.202	Obvious deviation from Laboratory Manual or error in laboratory data (HT-SBA)	Day 6 (follow on) Day 66 (naive)						EXC

PD code	PD Description	Study objective/ period	FAS IMM Persistence (Day 1)	FAS IMM (Day 31)	FAS IMM (Days 6, 31/Days 66,	PPS IMM Persistence (Day 1)	PPS IMM (Day 31)	PPS IMM (Days 6, 31/Days 66,
112.302	Obvious deviation from Laboratory Manual or error in laboratory data (HT-SBA)	Day 31			91)		EXC	EXC (follow on only)
112.502	Obvious deviation from Laboratory Manual or error in laboratory data (HT-SBA)	Day 91						EXC (naive only)
120.100	Randomization failure to treatment	Day 1				EXC (naive only)	EXC (naive only)	EXC (naive only)
140.100	Vaccination not according to protocol	Day 1				EXC	EXC	EXC
140.300	Vaccination not according to protocol	Day 61 (Naive only)						EXC (naive only)
150.100	Administration of forbidden vaccine	Day 1 (before BS_1)				EXC	EXC	EXC
150.300	Administration of forbidden vaccine	Day 1 (after BS_1)- day 7					EXC	EXC
150.500	Administration of forbidden vaccine	-7/+7 2 nd vaccination (naive only)						EXC (naive only)
200	Subject did not meet entry criteria	Day 1 – end of study				EXC	EXC	EXC

PD code	PD Description	Study objective/ period	FAS IMM Persistence (Day 1)	FAS IMM (Day 31)	FAS IMM (Days 6, 31/Days 66, 91)	PPS IMM Persistence (Day 1)	PPS IMM (Day 31)	PPS IMM (Days 6, 31/Days 66, 91)
220	Subject had contraindication for a subsequent study vaccination but was vaccinated	Day 1- Day 61 (naive only)						EXC
230.101	Administration of forbidden medication	Day 1				EXC	EXC	EXC
230.102	Administration of forbidden medication: ANTIBIOTICS	Day 1 (before BS_1)				EXC		
230.201	Administration of forbidden medication	Day 6 (follow on) Day 66 (naive)					EXC (follow on only)	EXC
230.202	Administration of forbidden medication: ANTIBIOTICS	Day 6 (follow on) Day 66 (naive)						EXC
230.301	Administration of forbidden medication	Day 31					EXC	EXC
230.302	Administration of forbidden medication: ANTIBIOTICS	Day 31 (before BS_2)					EXC	EXC (follow on only)
230.501	Administration of forbidden medication	Day 91						EXC (naive only)
230.502	Administration of forbidden medication: ANTIBIOTICS	Day 91						EXC (naive only)

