240	Underlying medical condition forbidden by the protocol	Day 1- end of study				EXC	EXC	EXC

$\sim$	~		
Con	†10	en:	tıa.
COL		$\iota\iota\iota\iota\iota$	ши.

PD code	PD Description	Study objective/ period	FAS IMM Persistence (Day 1)	FAS IMM (Day 31)	FAS IMM (Days 6, 31/Days 66, 91)	PPS IMM Persistence (Day 1)	PPS IMM (Day 31)	PPS IMM (Days 6, 31/Days 66, 91)
260.100	Did not comply with study vaccination schedule	Day 1					EXC	EXC
260.200	Did not comply with study vaccination schedule	Day 61 (naive only)						EXC
270.100	Did not comply with blood draw schedule*	Day 1				EXC		EXC
270.200	Did not comply with blood draw schedule	Day 6 (follow on) Day 66 (naive)						EXC
270.300	Did not comply with blood draw schedule*	Day 31					EXC	EXC (follow on only)
270.400	Did not comply with blood draw schedule	Day 91						EXC (naive only)

\*e.g. BD after vaccination

FAS = Full Analysis Set; PPS=Per Protocol Set; EXC = excluded from this analysis set.

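### Deviation codes differ between SAP 6.1/4.1.1 and Table 7.7; the table has no row for code 250, and its code 140.100 drops subjects from the persistence per-protocol set without a stated reason

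*SAP*

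**What the plan says.** SAP 6.1 sorts the CSR-reportable deviations into categories and attaches codes. It uses 140.x twice: "Vaccine administration not according to protocol (PD code 140.x" stands in the category for a wrong vaccine or dose, and "Subject did not comply with study vaccination schedule (PD code 140.x" stands in the category for key study procedures. It also lists "Concomitant infection related to the vaccine which may influence immune response (PD code 250". It states that every CSR-reportable deviation removes the subject, or part of the subject's data, from at least one analysis set. Code 260 does not appear in 6.1.

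SAP 4.1.1 gives, as one example of a vaccination error, "Subjects got vaccinated with the correct vaccine but containing a lower volume (PD code 140.3", and refers the reader to section 7 for how such errors are handled. SAP 6.2 says the deviation listings are programmed from the section 7.7 table, using the codes in its first column.

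In SAP 7.7, codes 140.100 (Day 1) and 140.300 ("Day 61 (Naive only") mean "Vaccination not according to protocol". Codes 260.100 (Day 1) and 260.200 (Day 61, naive subjects) mean "Did not comply with study vaccination schedule". There is no code 140.3 and no row for 250.

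Protocol 8.3.5 sets the vaccination condition for the persistence per-protocol set: "Correctly receive all meningococcal vaccinations in the parent study (persistence objective". SAP 7.4 repeats it. In both places the extension-study vaccinations enter only for the other immunogenicity objectives. Both also require that the subject has no deviation leading to exclusion. Protocol 3.5.1 and 5.2 place the Day 1 blood draw before the Day 1 vaccination.

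**The concern.** The code decides which analysis sets a subject leaves, so the codes in the SAP's text and those in its table need to agree, and the table needs to cover what the text promises. They do not agree. Timetable deviations carry one code in 6.1 and another in 7.7. The low-volume code in 4.1.1 is not in the table. One deviation that 6.1 calls exclusionary has no row at all.

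The table also removes from the persistence per-protocol set a subject whose Day 1 injection was given incorrectly, although nothing about that injection can alter a sample already taken. At stake is the composition of the per-protocol sets, including the one that supports the primary persistence objective. It also matters whether the exclusion program, which SAP 16 marks for peer review, can be checked against a single definition.

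**Working it through.** No sample size, power or alpha figure is involved. The check sets the rows of the SAP 7.7 immunogenicity table side by side, where EXC means excluded and a dash means kept.

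| Code | Deviation | When | PPS Persistence | PPS Day 31 | PPS Days 6, 31/66, 91 |
|---|---|---|---|---|---|
| 140.100 | vaccination error | Day 1 | EXC | EXC | EXC |
| 260.100 | timetable | Day 1 | – | EXC | EXC |
| 140.300 | vaccination error | Day 61 | – | – | EXC (naive) |
| 260.200 | timetable | Day 61 (naive) | – | – | EXC |
| 100 | no study vaccine given | Day 1 to end of study | – | EXC | EXC |
| 150.300 | forbidden vaccine after the Day 1 sample | to Day 7 | – | EXC | EXC |
| 120.100 | randomization failure | Day 1 | EXC (naive) | EXC (naive) | EXC (naive) |
| 270.100 | blood draw timing | Day 1 | EXC | – | EXC |
| 250 | concomitant infection | no row | no row | no row | no row |

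1. **Timetable code.** 140.100 and 260.100 differ in one cell, PPS Persistence. 140.300 and 260.200 have the same pattern. The 6.1 label could therefore matter only for a Day 1 deviation, and only if 140.x were read as 140.100. SAP 6.2 points to the table's codes, under which the deviation is 260.100 and the subject is kept in PPS Persistence.

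2. **Category summary.** SAP 6.1 promises counts by deviation category. With 140.x in two categories and 260 in none, a 260.x deviation has no assigned category. Following the 7.7 table does not settle this.

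3. **Code 250.** 6.1 says such a deviation excludes from at least one set. The table names none, and listings programmed from the table would not pick it up.

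4. **Code 140.100 and PPS Persistence.** The sample precedes the injection. A subject never vaccinated in the extension (code 100), or given a forbidden vaccine after the Day 1 sample (150.300), stays in PPS Persistence. A subject whose Day 1 dose was given incorrectly leaves it. All three can have the same kind of pre-vaccination sample. A sample drawn after vaccination is the table's own example under 270.100, so 140.100 is not needed for that case. Code 120.100 raises the same question for naive subjects.

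5. **Full Analysis Set.** Codes 140, 260 and 120 have no EXC in any FAS column, and the FAS definitions in SAP 7.3 carry no deviation clause.

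**The case against.** The strongest reply is that the SAP already says which list governs: 6.2 ties the listings to the 7.7 codes, and 4.1.1 defers to section 7. This stands. A reader might infer from 6.1 that the same timetable deviation is kept in or dropped from the persistence set according to the section followed. The documents do not support that, because 6.2 settles the choice. For an out-of-window Day 1 visit, 270.100 may also remove the subject under either code, if that code covers visit timing; the SAP does not say whether it does.

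A reader might also infer from 140.3 that an under-volume Day 1 booster would stay in the Day 31 per-protocol set. That does not follow. Row 140.100 covers Day 1 for all groups and excludes from that set, equating 140.3 with 140.300 is a guess about suffixes, and the per-protocol definition separately requires correct receipt of the relevant extension vaccinations.

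On code 250, it would be too strong to say that it can never be applied. The clinical and study-delivery leads assess deviations under 6.2, and a signed Exclusion Memo precedes the analysis under 6.1. Those routes could catch a case, but they do not supply the missing rule on which sets it leaves.

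On 140.100, the persistence set also requires that there be no deviation leading to exclusion, so the table does not formally contradict the definition. For 120.100, SAP 4.1.1 says in general terms that misrandomized subjects leave the per-protocol set. Both points stand. What remains is that the 140.100 exclusion has no stated reason and sits badly beside the treatment of codes 100 and 150.300.

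**Conclusion.** The code inconsistencies are real, and two faults survive when the 7.7 table is followed to the letter: code 250 has no row, and 140.100 removes subjects from PPS Persistence for an event after the sample. The second rests on the Day 1 sample being taken before the injection, as the protocol requires.

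The effect is small and confined to the per-protocol analyses. Protocol 8.4.2.2.2 names the Full Analysis Set for the primary objective, and it does not change; there are no hypotheses or success criteria that could turn on the per-protocol result. The documents give no expected number of deviations, so the loss cannot be sized. Purely as an assumption, losing 5 of 100 subjects would widen an interval for a mean by √(100/95) = 1.026, or about 2.6%. Nothing in the documents suggests that this many would be affected.

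**What to change.** - Add a row for code 250 to the SAP 7.7 table, stating which per-protocol sets it excludes from.
- Remove the PPS Persistence exclusion for 140.100, or state why it stays. Its exclusions from the other two per-protocol sets have their own cells and can remain. Review 120.100 on the same logic, and if it changes, bring the general sentence in SAP 4.1.1 into line.
- In SAP 6.1, change the code for timetable deviations to 260.x, so that each code belongs to one category.
- In SAP 4.1.1, replace 140.3 with the matching table codes: 140.100 for Day 1 and 140.300 for Day 61.
- State whether 270.100 covers a Day 1 visit outside its window.

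The cost is a few wording and table edits, with no new data or analysis, provided they are made before the exclusion program is run and the Exclusion Memo is signed.
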